7.2 Secondary criteria

7.2.1 Efficacy

- Progression-free survival (PFS) measured from the date of treatment initiation to the date of progression or death, whichever comes first. Patients alive and free of progression at the cut-off date will be censored at the last assessment date.
- Modification of the size of the irradiated and non irradiated lesion(s) as measured by its longest diameter according to RECIST 1.1 will be compared.

Assessment of efficacy endpoint listed below will be performed according to RECIST v 1.1 criteria (refer to Appendix 4: RECIST 1.1 CRITERIA) and modified RECIST (mRECIST) (refer to Appendix 5: mRECIST CRITERIA MODIFIED RESPONSE EVALUATION CRITERIA IN SOLID TUMORS).

Efficacy endpoints are:

- Disease Control Rate (DCR): complete responses (CR) + partial responses (PR) + stable disease (SD).
- Objective Response Rate (ORR): CR + PR
- Duration of response (DOR)
- Time to progression (TTP) of non irradiated lesions is computed as the delay from enrollment to the first occurrence of progression outside of the irradiated field
- Time to progression (TTP) of irradiated lesions is computed as the delay from enrollment to the first occurrence of progression of irradiated lesions;
- Evaluation of the local control, distant control.

In lung cancer and sarcoma patients receiving a second SABR course:

For patients in lung and sarcoma cohorts who can receive a second SABR course if oligoprogression, the objective response rate at 6 weeks is defined as any partial or complete response according to RECIST v1.1 observed at the first radiological evaluation (6 weeks after the second SABR course) over the number of patients that received a second SABR course.

- Size of the irradiated and non irradiated lesion(s) is measured in its longest diameter according to RECIST 1.1. Modification observed between the time of progression 1 and the value at 6 weeks will be compared between irradiated and non irradiated lesions.

- Progression-free survival 2 (PFS2) measured from the date of the second SABR course to the date of second progression or death. Patients alive and free of progression at the cutoff date will be censored at the last assessment date.
- Time to progression ratio (TTPr) in patient that received a second SABR course. To define the TTP ratio, let's denote:
 - o TTP1 the time from treatment initiation to the time of progression after first irradiation

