8 DETERMINATION OF SAMPLE SIZE AND STATISTICAL ANALYSIS

8.1 Sample size

One-year progression-free survival will be estimated in CRC (cohort 1, *closed to inclusions*), in NSCLC (cohort 2, *closed to inclusions*), in RCC (cohort 3, *closed to inclusions*) and in sarcoma (cohort 4, *closed to inclusions*). Within each cohort, a Fleming 1-stage design will be applied to demonstrate that the progression free survival rate at one year is not inferior to 15% but could reach 32%.

To ensure a global alpha risk (Type I error) will be fixed at 0.1 (unilateral), the Bonferroni correction will applied: Out of the 4 cohort, one (RCC cohort) has been closed for lack of accrual and no test will be carried out in this cohort. Therefore, the alpha risk for each test will be 0.033.

To test in each cohort, the hypothesis that the PFS rate is greater than p0 with alpha=0.033 and with a 90% power to detect activity greater than p1, we need to enroll 54 evaluable patients.

If 13 patients or more are alive and free of progression at one year in the cohort, the combined SABR+ atezolizumab will be considered as a success for the corresponding histology.

To take into account a possible rate of 10% of non evaluable patients, and considering that the renal cohort will close after the enrolment of 7 patients, the total number of patients will be 187 = 3 * 60 + 7 to achieve 162 evaluable patients total in the 3 opened cohorts.

In lung cancer and sarcoma patients receiving a second SABR course:

A group of NSCLC and sarcoma patients progressing after their initial treatment with SABR+atezolizumab will be enrolled for a second SABR course. Assuming that up to 50% of patients may display a oligoprogression (i.e. being eligible for a second SABR course), after immune checkpoint blockers, between 25 and 30 patients per cohort are expected to receive a second SABR course. These cohorts size will enable to detect a response rate at 6 weeks of p1=30% versus a response rate below p0=10% at the 10% type I error level (one-sided) and with a 90% power. In each cohort, if 5 or more responses are observed, the second SABR course will be considered as promising. This threshold will be recomputed based on the actual number of patients re-irradiated in each cohort.

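### The 90% power stated for 25 to 30 re-irradiated patients per cohort is not reached at 26, 27 or 28 patients, where exact power is 84% to 89%

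*Protocol*

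**What the plan says.** Protocol section 8.1 plans a response-rate assessment after the second SABR course, separately in the NSCLC and sarcoma cohorts. The expected size is given as "between 25 and 30 patients per cohort are expected to receive a second SABR course". It rests on an assumption about eligibility: "Assuming that up to 50% of patients may display a oligoprogression".

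The operating characteristics are claimed for that range as a whole. "These cohorts size will enable to detect a response rate at 6 weeks of p1=30% versus a response rate below p0=10" (percent) is followed by "at the 10% type I error level (one-sided) and with a 90% power". The synopsis makes the same claim under sample size determination.

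Section 8.1 then adds a decision rule: "In each cohort, if 5 or more responses are observed, the second SABR course will be considered as promising". The next sentence qualifies it: "This threshold will be recomputed based on the actual number of patients re-irradiated in each cohort". Section 7.2.1 defines the response rate as responders "over the number of patients that received a second SABR course", so the sample size for this rule is the number actually re-irradiated.

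**The concern.** The claim attaches one pair of error rates to six possible sample sizes. The test is a count of responses in a small group, so its true error rates move in steps. Each time the threshold rises by one response, alpha drops well below its limit and power drops with it. A design that just meets 10% and 90% at one size need not meet them a patient or two later.

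The printed threshold of 5 fits the bottom of the range, so the question is what happens just above it. If power is lower there, a result short of the threshold would be read as coming from a 90% power rule when the chance of missing a true 30% response rate is above 10%.

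**Working it through.** **Inputs** (Protocol section 8.1): n = 25 to 30 per cohort; p0 = 0.10; p1 = 0.30; alpha 0.10 one-sided; power 0.90; printed threshold r = 5, to be recomputed for the actual n.

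**Formula.** With X the number of responders among n, the exact tail probability is P(X ≥ r | n, p) = Σ C(n,k) p^k (1−p)^(n−k), summed over k = r to n. Alpha is this at p = 0.10 and power is this at p = 0.30. For each n, take the smallest r with alpha ≤ 0.10.

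**Step 1: reproduce the stated design.** At n = 25 and r = 5, alpha = 0.0980 and power = 0.9095. The printed threshold and both error rates agree at the lower end of the range.

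**Step 2: the whole range, with the threshold recomputed.**

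| n | r | exact alpha | exact power | 90% reached? |
|---|---|---|---|---|
| 25 | 5 | 0.0980 | 0.9095 | yes |
| 26 | 6 | 0.0399 | 0.8374 | no |
| 27 | 6 | 0.0471 | 0.8642 | no |
| 28 | 6 | 0.0550 | 0.8872 | no |
| 29 | 6 | 0.0637 | 0.9068 | yes |
| 30 | 6 | 0.0732 | 0.9234 | yes |

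**Step 3: can another threshold rescue 26 to 28?** Keeping r = 5 gives alpha 0.1118, 0.1266 and 0.1421 at 26, 27 and 28, all above 0.10. A threshold above 6 lowers power further. No threshold meets both criteria at these three sizes.

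**Step 4: size of the shortfall.** 90 − 83.7 = 6.3 points at 26; 90 − 86.4 = 3.6 at 27; 90 − 88.7 = 1.3 at 28.

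**Step 5: a likely origin of the blanket claim.** The one-stage normal approximation gives n = [(1.2816 × √(0.10 × 0.90) + 1.2816 × √(0.30 × 0.70)) / 0.20]² = [(1.2816 × 0.7583) / 0.20]² = 23.6, so 24 patients. Its approximate power, Φ{[0.20√n − 1.2816 × 0.30] / 0.4583}, runs from 0.910 at n = 25 to 0.940 at n = 30. By that formula the whole range looks adequate, because it ignores the step in the threshold at 26.

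**Step 6: just outside the range.** With r = 5, power is 0.889 at n = 24 and 0.763 at n = 20.

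**The case against.** The strongest defence is that little is lost. The design reproduces at 25, 29 and 30; 28 misses by only 1.3 points; and the dip at 26 and 27 is the ordinary sawtooth of an exact test. At those two sizes alpha is only 4.0% and 4.7%, so the rule errs on the cautious side. The endpoint is secondary in a non-comparative phase II trial. All of this stands and sets the weight of the point. It does not make the sentence true for 26 to 28 patients. The normal approximation explains the sentence, but the rule is a count and its error rates are the exact ones.

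Stronger readings are tempting and are not supported:

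- A reader might infer that 5 responses would be applied at every size, which at 30 patients would mean alpha of 17.6%. Section 8.1 says that the threshold will be recomputed, so that situation should not arise.
- A reader might infer that the power claim is also false below 25 patients. The protocol states no power there, so there is nothing to contradict.
- A reader might take 25 to 30 as a pure ceiling, with any share under 50% falling below 25. It does not: 25 is 41.7% of 60 enrolled (25/60) or 46.3% of 54 evaluable (25/54).
- A reader might take 27, half of 54, as the plan's central case. The plan names none, and half of 60 enrolled is 30, where power is 92.3%.

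**Conclusion.** The concern holds in a limited form. The claim of 10% one-sided type I error with 90% power is correct at 25, 29 and 30 patients and incorrect at 26, 27 and 28, where power is 83.7%, 86.4% and 88.7%. The shortfall is material only at 26 and 27. Type I error is not at issue once the threshold is recomputed.

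This rests on two assumptions: that the recomputation takes the smallest threshold with exact alpha of at most 10%, which section 8.1 does not spell out, and that the denominator is every patient re-irradiated in the cohort, as section 7.2.1 defines it. Fleming's rounded cut-off (n·p0 + z√(n·p0·(1−p0)), to the nearest integer, plus one) also gives 5 at n = 25 and 6 at n = 26 to 30, so the result does not depend on choosing the exact rule over that one. Severity is minor.

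**What to change.** In section 8.1, and in the matching sentence of the synopsis, replace the single power figure. State that the threshold is the smallest number of responses keeping exact one-sided alpha at or below 10%; that this is 5 or more at 25 patients and 6 or more at 26 to 30; and that exact power against a 30% response rate is then about 84% to 92%, depending on the number re-irradiated. The figure of 5 should stay, tied to 25 patients.

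Optionally, add that 25 to 30 rests on an assumption of up to 50% oligoprogression, and that power is below 90% if fewer than 25 are re-irradiated (0.889 at 24 and 0.763 at 20).

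The cost is wording only. No procedure, endpoint or patient number changes. The one downside is a slightly less favourable stated power.

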8.2 Stopping rule

Safety and feasibility will be carefully monitored and strict statistical stopping rules will be implemented. The following limiting events will be considered for the first 20 patients (all cohorts combined together:

- Any toxicity of grade 4 and above
- Any toxicity leading to treatment interruption more than 2 cycles.

The approach developed by Kramar and Molevi (2009) will be used to define stopping boundaries. The maximum acceptable rate of limiting event is defined as 20%. This gives the following stopping rules for the first patients (across all cohorts):

Stop if

Number of events	2	3	4	5	6	7
in less than (n _k assessable pts)	2	4	8	11	15	18

8.3 Data Analysis

8.3.1 General Considerations

- Statistical analysis for this study will be the responsibility of the Sponsor. For continuous variables, summary statistics will include number of patients, mean, standard deviation, median, interquartile range, minimum, and maximum. Categorical endpoints will be summarized using number of patients and frequency in %. Missing data will not be imputed.
- The interpretation of the study results will be the responsibility of the investigators, pharmacokineticist and statistician.
- Exploratory analyses of the data not described below will be conducted as deemed appropriate.

8.3.2 Efficacy Analysis

Progression free survival (PFS) is defined as the time from treatment initiation to first documentation of tumour progression or to death, whatever the cause of death, whichever occurs first. Any patient that discontinues due to a reason other than progressive disease (for example, AE, patient/investigator decision) will have their time-to-event data either censored at

the follow-up visit if no progressive disease is found during this visit, or censored at the date of the last objective progression-free disease assessment if progressive disease is found at the follow-up visit. The progression will be assessed using RECIST v 1.1 and mRECIST.

Time to progression of non irradiated lesions is computed as the delay from enrollment to the first occurrence of progression outside of the irradiated field. Time to progression of irradiated lesions is computed as the delay from enrollment to the first occurrence of progression of irradiated lesions.

The disease Control Rate (DCR) will be defined as the sum of complete responses (CR), partial responses (PR) and stable disease (SD). The objective Response Rate (ORR) will be defined as the sum of complete responses (CR) and partial responses (PR).

The PFS, DCR, ORR and DOR will be computed by patient. In each cohort, response rates with exact 95% confidence intervals will be provided, and PFS and duration of response will be estimated using Kaplan-Meier survival method and presented with Rothman's 95% Confidence Intervals. Median follow-up will be estimated using inverse Kaplan-Meier method (Collet D., 1994). Secondary analysis will investigate the impact of the number of metastatic sites in 2 modalities (<5 and ≥5). A semi-parametric Cox model stratified on the cohort and adjusted for the number of metastasis will be developed.

The TTP ratio (TTPr) will be computed in all patients receiving a second SABR course, as the ratio of TTP2 over TTP1. Patients receiving a second SABR course without a documented progression 1 will not be included. Patients dying without documented second progressions will be counted as progressions at the date of death considering the very poor prognosis of those patients. Censored TTP2 will make the TTPr censored too. In this case, the Kaplan-Meier approach will be used to derive values of TTPr. For instance, rate of patients with TTPr greater than 1.5 will be computed, among other thresholds (1.33, 1.5, 2).

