3.2 Follow-up period

- Patients who discontinue atezolizumab for other reason than disease progression
 will have follow up visit every 3 months up to 12 months or disease progression,
 whichever occurs first, for assessment of disease progression and collection of delayed
 toxicities.
- Patients who discontinue atezolizumab for disease progression will have an end of study visit 1 month after treatment discontinuation.

The end of the trial is defined as being the last protocol-specified visit of the last patient, *i.e* the last visit of the last patient during the follow-up period (up to 12 months after atezolizumab discontinuation) or the last attempt by the investigator to schedull this visit for the last patient.

During the follow-up period, patients are allowed to receive another anticancer therapy.

3.3 Flowchart:

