7 EVALUATION CRITERIA

7.1 Primary criterion

In each cohort, progression-free survival rate at one year is defined as the rate of patients alive and free of progression at one year from treatment initiation. Progression is defined using RECIST 1.1. criteria, or death, whatever the cause of death, whichever occurs first.

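### Section 8.3.2 censors a progression found at follow-up after a patient stops for another reason, contradicting the PFS definition and biasing Kaplan-Meier PFS upward

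*Protocol*

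**What the plan says.** Section 8.3.2 defines PFS as the time from treatment initiation to "first documentation of tumour progression or to death, whatever the cause of death, whichever occurs first". The next sentence covers "Any patient that discontinues due to a reason other than progressive disease (for example, AE, patient/investigator decision"). It gives these patients two outcomes, and both are censoring. With a clean scan, the date used is "the follow-up visit if no progressive disease is found during this visit". The second outcome applies when the scan shows progression, and the patient's time is still not an event: "or censored at the date of the last objective progression-free disease assessment if progressive disease is found at the follow-up visit". PFS is then estimated by Kaplan-Meier.

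Section 7.2.1 defines the same secondary criterion as "Progression-free survival (PFS) measured from the date of treatment initiation to the date of progression or death, whichever comes first" and limits censoring to progression-free patients: "Patients alive and free of progression at the cut-off date will be censored at the last assessment date". The synopsis has the same rule.

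Section 3.2 says that patients who stop for a reason other than progression "will have follow up visit every 3 months up to 12 months or disease progression", and gives the assessment of progression as one purpose of those visits. Section 6.3 schedules a CT scan at each of them.

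The primary criterion is separate. In section 7.1 the "progression-free survival rate at one year is defined as the rate of patients alive and free of progression at one year from treatment initiation". Section 8.1 calls a cohort a success if at least 13 patients meet this, with 54 evaluable patients planned.

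**The concern.** Kaplan-Meier estimation assumes that a censored patient has the same future risk as those still under observation. Here the patient is censored because progression was found, and the censoring is dated back to before it. A known failure leaves the risk set without being counted.

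The rule is also asymmetric. A clean scan earns the patient progression-free time up to the visit. A scan showing progression is turned into an earlier censoring. Both features favour the treatment in the reported PFS curve and its one-year value. Section 8.1 sets that one-year rate against reference values of 15% and 32%, only 17 points apart, so a shift of a few points matters for interpretation.

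**Working it through.** **1. The text, side by side.** Take a patient who stops for toxicity and whose progression is found at a later follow-up scan.

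| Place | Treatment of that progression |
|---|---|
| 8.3.2, definition | Event |
| 7.2.1 and synopsis | Event (only patients alive and progression-free are censored) |
| 3.2 and 6.3 | The visit and CT take place in order to find it |
| 8.3.2, next sentence | Censored at the last progression-free assessment |

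The last row cannot be reconciled with the others. It does not depend on the start of a new anticancer therapy, although section 3.2 allows one during follow-up.

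**2. The plan's design figure.** No stated figure is disputed. The size in section 8.1 reproduces by the normal approximation, with p0 = 0.15, p1 = 0.32, one-sided alpha 0.10/3 = 0.033 and power 90%:

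n = [(z(0.967)·√(0.15·0.85) + z(0.90)·√(0.32·0.68)) / 0.17]² = 54.3, against 54 stated; 54/0.90 = 60 enrolled.

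**3. Size of the Kaplan-Meier bias.** The share stopping for other reasons is not given, so it is varied. Simulation, 40,000 patients per scenario:
- Progression: constant hazard giving a true 52-week rate of 15% or 32%.
- Scans on treatment (section 6.2: weeks 4, 7, 13, then every 12 weeks): 3, 6 and 12 weeks after start, then every 12 weeks.
- Discontinuation for other reasons: independent of progression, with a 12-month probability of 10 to 40% in the absence of progression.
- Follow-up (section 3.2): four visits, 13 weeks apart.
- Written rule: progression at follow-up is censored at the last clean assessment, including any clean follow-up visit. Corrected rule: it is an event at the visit that finds it.

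| True rate | 12-month discontinuation | Share actually stopping first | KM at 52 weeks, written rule | KM, corrected rule | Difference (points) |
|---|---|---|---|---|---|
| 15% | 10% | 6.2% | 18.2% | 17.3% | 0.9 |
| 15% | 20% | 12.2% | 19.6% | 17.7% | 1.9 |
| 15% | 30% | 18.4% | 21.3% | 18.0% | 3.3 |
| 15% | 40% | 24.3% | 23.2% | 18.5% | 4.7 |
| 32% | 10% | 9.5% | 36.6% | 35.4% | 1.2 |
| 32% | 20% | 18.3% | 38.3% | 35.4% | 2.9 |
| 32% | 30% | 26.2% | 40.6% | 36.1% | 4.5 |
| 32% | 40% | 34.3% | 43.1% | 36.3% | 6.8 |

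With no such discontinuation the two rules agree (17.3% and 34.9%). These values exceed 15% and 32% because the last scan before week 52 is at week 48: 0.15^(48/52) = 0.174 and 0.32^(48/52) = 0.349. Across 10 to 40% discontinuation, the written rule deletes the progression of 5.4 to 21.2% of all patients at a true rate of 15%, and of 6.7 to 24.3% at 32%. Within 52 weeks the shares are 3.3 to 14.0% and 2.7 to 12.2%. A progression found after week 52 but censored before it works slightly the other way; the simulation includes this, and the net effect is upward in every scenario.

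**4. The primary endpoint.** There are two conditional cases, neither of which the protocol states.
- If these patients were dropped as non-evaluable, the descriptive rate would rise (for example 8/54 = 14.8% to 8/50 = 16.0%). The count stays at 8, and the threshold of 13 is no closer.
- If a share q of true progressors were scored as progression-free, the success probability per patient at a true rate of 15% becomes 0.15 + 0.85q. For q = 2%, 5% and 10% this is 0.167, 0.1925 and 0.235. The exact chance of at least 13 of 54 then rises from 0.053 to 0.105, 0.229 and 0.513. (That 0.053 already exceeds 0.033 is a separate matter.)

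**The case against.** The best defence concerns scope. What is directly damaged is Kaplan-Meier PFS, a secondary criterion in a non-comparative phase II trial. The primary criterion is a count of patients alive and progression-free at one year, with no censoring in its definition. This stands, and it limits the weight of the point.

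A second defence is that some plans deliberately censor at treatment discontinuation or at new therapy. This sentence does neither: it is not conditional on new therapy, and the censoring date depends on what the scan shows. Nor can the matter be left to the statistical analysis plan. The protocol itself states the rule, so a plan that follows it inherits the bias and one that departs from it contradicts the protocol.

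Third, the size rests on an assumed discontinuation rate, and the upper scenarios are large. This is fair, and the result should be read as a range.

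Three stronger readings are tempting but not supported:
- A reader might infer that these known failures become non-evaluable for the primary endpoint. Section 8.1 does not tie evaluability to section 8.3.2, whose sentence concerns time-to-event data. Dropping failures would also leave the count of successes unchanged.
- A reader might set the written rule against the 17.3% obtained with no discontinuation. That overstates the effect: part of the gap arises because progression is found later on the follow-up schedule. The proper comparator is the corrected rule.
- A reader might take the singular follow-up visit to mean that progression-free patients are censored at the first of up to four. Read with sections 3.2, 6.3 and 7.2.1, it is loose wording, not a demonstrated second bias.

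**Conclusion.** The point holds for Kaplan-Meier PFS. Section 8.3.2 turns a documented progression into a censoring, against its own definition and against sections 3.2, 6.3 and 7.2.1, and nothing elsewhere in the protocol corrects this. The resulting bias in one-year Kaplan-Meier PFS is about 1 to 5 points at a true rate of 15% and about 1 to 7 points at 32%. These figures assume constant hazards, discontinuation independent of progression, and 10 to 40% stopping for other reasons by 12 months; with none stopping there is no bias. The primary decision is not shown to be affected. It would be only if one-year status were taken from the censored data, which the protocol neither states nor excludes.

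**What to change.** Replace the discontinuation sentence in section 8.3.2 with wording such as: patients who stop for a reason other than progression remain in follow-up; progression found at any follow-up visit is a PFS event at the date it is documented, and death is an event at its date; only patients alive and progression-free are censored, at their last tumour assessment.

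Add one line stating that, for the primary endpoint, such progressions or deaths within one year of treatment initiation count as failures. Censoring at discontinuation or at new anticancer therapy may be kept as a sensitivity analysis, labelled as such.

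The cost is a short text amendment, matched in the statistical analysis plan. No new data are needed, because section 6.3 already schedules these scans.
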